### **8.3 Method of Assigning Subjects to Treatment Groups**

In Phase 1, subjects who meet the eligibility criteria will be enrolled in the dose level that is open to enrollment by the IRT system. In Phase 2, subjects will be enrolled into the cohort by tumor type by the IRT system.

### **8.4 Blinding/Unblinding**

This study is not blinded.

### **8.5 Concomitant Treatments**

Any medication(s), including those taken within 30 days prior to the first dose of IMPs, throughout treatment with IMP, until the 30-day follow-up visit after the last dose of IMP or

until start of new anticancer therapy (whichever occurs first), and anytime thereafter if used to treat IMP-related SAEs will be recorded.

### **8.5.1 Permitted Concomitant Medications**

Subjects may receive medications to treat pre-existing conditions, IMP-related AEs, or IMP-unrelated AEs.

Subjects are permitted the use of topical, ocular, intra-articular, intranasal, and inhalational corticosteroids (with minimal systemic absorption). Adrenal replacement steroids are permitted. A brief (less than 3 weeks) course of corticosteroids for prophylaxis (e.g., contrast dye allergy) or for treatment of non-autoimmune conditions (e.g., delayed-type hypersensitivity reaction caused by a contact allergen) is permitted.

Immunosuppressive agents including steroids may be used to treat IMP-related AEs, as described in Section [8.2](#).

Concomitant palliative and supportive care for disease-related symptoms (including bisphosphonates and RANK-L inhibitors) is allowed if initiated prior to the first dose of study therapy.

The potential for overlapping toxicities with radiotherapy and the IMPs currently is not known. Therefore, palliative radiotherapy is not recommended while receiving IMPs. If palliative radiotherapy is required, then IMP should be withheld for at least 1 week before, during and 1 week after radiation. Subjects should be closely monitored for any potential toxicity during and after receiving radiotherapy, and AEs considered related to radiotherapy should resolve to Grade  $\leq 1$  prior to resuming IMP. Only non-target bone lesions without lung tissue included in the planned radiation field or CNS lesions may receive palliative radiotherapy while on study treatment.

### **8.5.2 Prohibited and/or Restricted Treatments**

While on study, subjects are not permitted to receive any additional experimental therapy or any therapy to treat the disease under study other than the IMP. Supportive therapy to manage symptoms or AEs is acceptable as noted in Section [8.5.1](#).

The following medications are prohibited during the study unless utilized to treat an AE:

- Immunosuppressive agents;
- Immunosuppressive doses of systemic corticosteroids, except as stated in Section [8.5.1](#);

- Any concurrent anti-neoplastic therapy (i.e., chemotherapy, hormonal therapy, immunotherapy, extensive, non-palliative radiation therapy, or standard or investigational agents for treatment of cancer).

Live-attenuated vaccines should not be administered during the treatment period and for at least 3 months after the last dose of IMP unless, according to the judgment of the Investigator in consultation with the Medical Monitor, the benefit of vaccination outweighs the hypothetical increased risk for an AE after vaccination. (As of Amendment 3, decisions regarding subject treatment should be made according to site standard of care as determined by the Principal Investigator.)

#### **8.5.3 Contraception**

Women of childbearing potential must use method(s) of contraception from the time of signing of the ICF, for the duration of study participation, and for 23 weeks after the last dose of IMP. This is calculated as 5 half-lives of nivolumab (half-life up to 25 days) plus 30 days (duration of ovulatory cycle). Men who are sexually active with woman of child-bearing potential must use method(s) of contraception from the time of signing of the ICF, for the duration of study participation, and for 31 weeks after the last dose of IMP. This is calculated as 5 half-lives of nivolumab plus 90 days (duration of sperm turnover).

During the screening period, the Investigator should review contraception methods and the time period that contraception must be followed with the subject. The individual methods of contraception for each subject (hormonal or barrier method of birth control; abstinence) should be determined in consultation with the Investigator.

#### **8.6 Treatment Compliance**

Subjects are administered the IMP(s) under direct supervision of study personnel.

### **9 STUDY PROCEDURES**

All efficacy, PK/PD, immunogenicity, and safety measurements obtained during the course of the study are summarized in [Table 9-1](#) and [Table 10.2-1](#). Procedures to be followed for subjects who are ongoing in the study (i.e., subjects who are continuing to receive study treatment or who are in safety or survival follow-up) at the time of data cutoff for completion of analyses are described in Section [9.5](#).

**Table 9-1 Schedule of Events: Screening and Treatment Periods**

Procedure b	Referenced Section(s) of Protocol	Screening	Cycle 1				Cycle 2		Cycle $\geq$ 3		EOT (Section 9.3)
			D1	D8	D15	D22	D1	D15	D1	D15	
Visit Window (days)		-28 to -1	-	$\pm 2$	$\pm 2$	$\pm 2$	-	$\pm 3$	-	$\pm 3$	
Written Informed Consent a	6.1 / 9.1	X									-
Inclusion/Exclusion Criteria	7.2 / 7.3	X									
Medical History/ Demographics	9.2.1	X									
Height		X									
Physical Examination, ECOG PS, and Body Weight	9.2.5	X	X				X		X		X
Pulse Oximetry	9.2.3		X		X		X	X	X	X	X
Vital Signs	9.2.3	X	X b	X c	X b	X c	X d	X d	X d	X d	X
12-lead ECG	9.2.4	X	X	X	X						X
Hematology Profile	9.2.2	X	X e	X	X	X	X e	X	X e	X	X
Serum Chemistry Profile	9.2.2	X	X e	X	X	X	X e	X	X e	X	X
Coagulation Profile	9.2.2	X	X e				X e		X e		X
Thyroid Function Testing	9.2.2	X					X e		X e		X
Urinalysis	9.2.2	X									X
Serum Pregnancy Testing (WOCBP)	9.2.2	X									X
Urine Pregnancy Testing (WOCBP)	9.2.2		X e				X e		X e		
Virus Testing	9.2.2	X									
Tumor Assessment, MRI or CT, including serum tumor markers, as applicable	9.2.6	X								X f	X
Tumor Biopsy	9.2.7	X g								X g	

**Table 9-1 Schedule of Events: Screening and Treatment Periods**

Procedure b	Referenced Section(s) of Protocol	Screening	Cycle 1				Cycle 2		Cycle $\geq$ 3		EOT (Section 9.3)
			D1	D8	D15	D22	D1	D15	D1	D15	
Visit Window (days)		-28 to -1	-	$\pm 2$	$\pm 2$	$\pm 2$	-	$\pm 3$	-	$\pm 3$	
Pharmacokinetics	10.2		Refer to Table 10.2-1								
Anti-drug Antibody			Refer to Table 10.2-1								
Pharmacodynamics			Refer to Table 10.2-1								
Adverse Events	10.3	X	X	X	X	X	X	X	X	X	X
Prior/Concomitant Medications	8.5	X	X	X	X	X	X	X	X	X	X
Mogamulizumab Administration	8.1.1		X	X	X	X	X	X	X	X	
Nivolumab Administration	8.1.1		X		X		X	X	X	X	

a: Informed consent must be obtained prior to undergoing any study specific procedure that is not part of normal care. Data from procedures that were done as part of normal care may be used once the subject signs the ICF, provided they were done within the screening window.

b: Pre-dose (up to 30 minutes before SOI); and EOI ( $\pm 5$  minutes) of nivolumab; predose (up to 30 min before) SOI, every 15 ( $\pm 5$  minutes) during infusion; and EOI ( $\pm 5$  minutes) of mogamulizumab; hourly during the 4-hour post-infusion observation period.

c: Pre-dose (up to 30 minutes before SOI) of mogamulizumab, every 15 ( $\pm 5$  minutes) during infusion, and EOI ( $\pm 5$  minutes) of mogamulizumab, 30 minutes ( $\pm 5$  minutes) after EOI of mogamulizumab.

d: Pre-dose (up to 30 minutes before SOI); and EOI ( $\pm 5$  minutes) of nivolumab; predose (up to 30 min before) SOI, every 15 ( $\pm 5$  minutes) during infusion; and EOI ( $\pm 5$  minutes) of mogamulizumab; 30 minutes ( $\pm 5$  minutes) after EOI of mogamulizumab.

e: Day 1 labs can be done up to 3 days prior to dosing.

f: Tumor assessments by RECIST v. 1.1 will be performed at Screening, at Week 10, at least every 12 weeks thereafter until unequivocal disease progression or death.

g: Required at Screening (except as indicated in the inclusion criteria) and at Week 10 (unless the tumor is inaccessible for biopsy).

h: Procedures to be followed for subjects who are ongoing in the study (i.e., subjects who are continuing to receive study treatment or who are in safety or survival follow-up) at the time of data cutoff for completion of analyses are described in Section 9.5.

CT=computed tomography; ECG=electrocardiogram; ECOG=Eastern Cooperative Oncology Group; EOI=end of infusion; EOT=End of Treatment; IMP=investigational medicinal product; MRI=magnetic resonance imaging; PS=performance status; RECIST=Response Evaluation Criteria in Solid Tumors; SOI=start of infusion; WOCBP=women of child-bearing potential.

**Table 9-2 Schedule of Events: Post-treatment Follow-up**

Procedure d	Referenced Section(s) of Protocol	Post Last Dose of IMPs Follow-up	
		30 Days	Day 100-110 and at Least Every 100 days Thereafter
Visit Window (Days)		± 5	
Serum Tumor Markers, as applicable	9.2.6	X a	X a
Tumor Assessment, MRI or CT	9.2.7	X a	X a
Adverse Events	10.3	X b	X b
Concomitant Medications	8.5/ 9.2.1	X c	X c
Survival Assessment, including Anticancer Therapies	6.3	X	X

a: Subjects who complete or discontinue treatment without disease progression will have tumor assessments collected at least every 12 weeks or per institutional standard of care until a new anti-cancer therapy is started, unequivocal disease progression is documented, or death.

b: AEs will be collected until 100 days after the last dose of IMP.

c: Concomitant medications usage will be collected until the 30-day follow-up visit after the last dose of IMP or until the start of new anticancer therapy (whichever occurs first), and anytime thereafter if used to treat IMP-related SAEs.

d: Procedures to be followed for subjects who are ongoing in the study (i.e., subjects who are continuing to receive study treatment or who are in safety or survival follow-up) at the time of data cutoff for completion of analyses are described in Section 9.5.

AE=adverse event; CT=computed tomography; IMP=investigational medicinal product; MRI=magnetic resonance imaging; SAE=serious adverse event.

## 9.1 Screening

No study-specific procedures that are not part of normal care may be initiated prior to the subject signing the informed consent in compliance with International Committee on Harmonisation-Good Clinical Practices (ICH-GCP) and local legislation. Screening evaluations used to determine the subject's study eligibility must be completed within 28 days prior to starting treatment unless otherwise specified. Data from procedures that were done as part of normal care may be used once the subject signs the ICF, provided they were done within the screening window.

At the Screening Visit, the Investigator will review the written ICF with each subject to ensure the understanding of the study and the study procedures. The subject, individual obtaining the ICF, will read, sign, and date/time the ICF and any other locally applicable documents. A photocopy of the signed ICF must be provided to the subject and the original document retained in the subjects source or study file. The date the screening procedures begin will be collected.

During the Screening period, the Investigator should review contraception methods and the time period that contraception must be followed. The individual methods of contraception for each subject (hormonal or barrier method of birth control; abstinence) should be determined in consultation with the Investigator.

Refer to the study-specific procedure manual for information to be collected for screen failures.

## **9.2 Baseline and Treatment**

### **9.2.1 Demographics, Medical History, Pre-treatment Adverse Events**

Subject demographics (race, ethnicity, gender), medical history, and current medical conditions will be recorded during the Screening Period. All relevant medical history, including currently active conditions and chronic conditions will be documented. Cancer history should include documentation of HPV or status of tumor for SCCHN. All pre-treatment AEs after signing ICF will also be documented.

### **9.2.2 Assessment of Safety Laboratory Parameters**

The central laboratory will provide the required materials for processing the samples, and will also provide instructions regarding centrifugation, processing, storage and shipment of samples (as outlined in a Laboratory Manual). The Investigator will receive a laboratory report for information on a per visit basis. Clinical significance including any related comments will be collected. As of Amendment 3, central laboratory analysis of samples will no longer be required (see Section 9.5); laboratory samples should be collected and analyzed in accordance with site standard of care procedures for the particular type of cancer.

Clinical laboratory parameters assessed in this study are displayed in [Table 9.2.2-1](#). Serum samples will be drawn for the determination of ADA as specified in [Table 10.2-1](#).

Any clinically important abnormal laboratory values noted during the Screening period will be recorded as medical history. If any post-treatment results are judged as being clinically significant by the Investigator, the Investigator should consider whether the result should be recorded as an AE. If deemed necessary, laboratory parameters may be retested or followed as unscheduled tests. Unscheduled tests should be performed by the central laboratory unless immediate results are required for the subject's safety. At minimum, the following laboratory abnormalities should be collected as an AE.

- Any laboratory test result that meets the criteria for a SAE;

- Any laboratory abnormality that requires the subject to have IMP discontinued or interrupted;
- Any laboratory abnormality that requires the subject to receive specific corrective therapy.

All clinically important abnormal laboratory tests occurring during the study will be repeated at appropriate intervals until (1) the value returns to baseline, (2) the value is judged to be clinically acceptable by the Investigator and the Sponsor, or (3) a diagnosis that explains the abnormal laboratory value is made. When possible, the Investigator should report the clinical diagnosis rather than the laboratory term (e.g., anemia versus low hemoglobin).

Clinical laboratory abnormalities that qualify as AEs and any events that lead to an intervention (including premature discontinuation of IMP or significant additional concomitant therapy), should be reported and evaluated as AEs.

**Table 9.2.2-1 Clinical Laboratory Assessments**

Laboratory Assessment	Test to be Performed		
Serum Chemistry	Alanine aminotransferase	Blood urea nitrogen	Lipase
	Aspartate aminotransferase	C-reactive protein	Sodium
	Albumin	Creatinine	Total bilirubin
	Alkaline phosphatase	Glucose	Total protein
	Amylase	$\gamma$ -Glutamyl transferase	Uric Acid
Thyroid Profile	Thyroid stimulating hormone	Free T4	Free T3
Coagulation Profile	Activated partial thromboplastin time		
Hematology	Hemoglobin	White blood cells	
	Hematocrit	Differential & absolute count	
	Red blood cells	Platelet count	
Urinalysis	Protein	Occult blood	
	Glucose	Urobilinogen	
Serum Pregnancy Test	To be performed for all women of childbearing potential (minimum sensitivity 25 IU/L or equivalent units of $\beta$ -human chorionic gonadotropin)		
Urine Pregnancy Test	To be performed for all female subjects of childbearing potential (minimum sensitivity 25 IU/L or equivalent units of $\beta$ -human chorionic gonadotropin)		
Virus Testing	HBs-Ag, HBs-Ab, HBc-Ab, HBV-DNA		
	Hepatitis C Ab and RNA		
	Human immunodeficiency virus		
	Cytomegalovirus serology (immunoglobulin G and M subclasses)		
Serum Tumor Markers, as Applicable	Disease-specific tumor markers		

HBs-Ag=hepatitis B surface antigen; HBs-Ab=hepatitis B surface antibody; HBc-Ab=hepatitis C surface antibody; HBV-DNA=hepatitis B virus deoxyribonucleic acid; RNA=ribonucleic acid.

### **9.2.3 Vital Signs**

Blood pressure and pulse rate measurements will be performed at each visit identified in [Table 9-1](#). Blood pressure and pulse rate will be performed after the subject has been resting for at least 5 minutes. Pulse oximetry will be performed prior to the infusion of nivolumab at each visit identified in [Table 9-1](#). Any new clinically relevant findings that are identified will be reported as AEs.

### **9.2.4 Electrocardiograms**

The subject will be supine for at least 5 minutes before the 12-lead ECG is performed. The 12-lead ECGs will be performed during the Screening period, on Days 1, 8, and 15 of Cycle, 1 and at EOT. All 12-lead ECGs recorded during the study will be obtained in triplicate (all three 12-lead ECGs within a 5-minute time period). All 12-lead ECGs on dosing days must be performed prior to infusion of first IMP and at the end of infusion ( $\pm$  10 minutes) of mogamulizumab. In case of clinically significant 12-lead ECG abnormalities including a non-screening 12-lead ECG that demonstrates a QTc value  $>$  500 msec or QTc interval change of  $>$  60 msec from baseline, 2 additional 12-lead ECGs should be obtained over a brief period (e.g., 30 minutes) to confirm prolongation. Additional 12-lead ECGs may also be performed as clinically indicated. The Investigator or designee has the responsibility to read and evaluate the 12-lead ECGs for the timely assessment of subject safety.

### **9.2.5 Physical Examination, Eastern Cooperative Oncology Group Performance Status, Height, and Body Weight**

The Investigator will perform a full physical examination during the Screening period and EOT visits. The complete physical examination requires assessment of the following categories: HEENT, heart, lungs, abdomen, skin, musculoskeletal, extremities, neurological, lymph nodes, and 'other'. Brief physical examination will be performed at the other timepoints specified in [Table 9-1](#). Brief physical examinations will be symptom directed. All significant abnormal findings during the Screening period will be recorded in the Medical History. New abnormal findings or worsening of baseline conditions detected at follow-up physical examinations will be recorded as AEs. A complete physical examination should also be performed when a subject discontinues the trial prematurely. Height will be documented during the Screening period; body weight and ECOG performance status will be measured as specified in [Table 9-1](#).

### **9.2.6 Disease-response Assessments**

High-resolution computed tomography (CT) with oral or iv contrast or contrast-enhanced magnetic resonance imaging (MRI) are the preferred imaging modalities for assessing radiographic tumor response. If a subject has a known allergy to contrast material, please use local prophylaxis standards to obtain the assessment with contrast if at all possible, or use the alternate modality. In cases where contrast is strictly contraindicated, a non-contrast scan will suffice. Screening assessments should be performed within 28 days of start of treatment and at other time points as specified in [Table 9-1](#). In addition to chest, abdomen and pelvis, all known or suspected sites of disease (including CNS) should be assessed during the Screening period and at subsequent assessments using the same imaging method and technique. If more than one method is used during the Screening period, then the most accurate method according to RECIST v. 1.1 should be used when recording data, and should again be used for all subsequent assessments. Bone scan, positron emission tomography scan, or ultrasound are not adequate for assessment of RECIST response. In selected circumstances where such modalities are the sole modality used to assess certain non-target organs, those non-target organs may be evaluated less frequently. For example, bone scans may need to be repeated only when CR is identified in target disease or when progression in bone is suspected. Subjects with signs of symptoms suggestive of brain metastasis should have an MRI of the brain.

Anti-tumor activity will be evaluated using RECIST v. 1.1 (See [Appendix 1](#)) and irRECIST v. 1.1. Evaluations will include serum tumor markers as applicable to the subject's tumor type. Tumor lesions planned for biopsy should not be used as target lesions for assessment of disease unless, in the opinion of the investigator, the procedure will not interfere with assessment of the subject's tumor status. New lesions should be measured and recorded.

For irRECIST v. 1.1 assessments, the following modifications of RECIST v. 1.1 apply:

- At each time point, the measurements of baseline-selected target lesions and new measurable lesions should be combined into the Total Measured Tumor Burden (TMTB), and one combined assessment provided.
- In order to be considered a new measurable lesion, a lesion must meet the same criteria as target lesions: a minimum 10 mm in the longest diameter for non-nodal lesions, and a minimum 15 mm in short axis for lymph nodes. Smaller new lesions contribute to the non-target or new nonmeasurable tumor burden, but do not get measured.
- Up to 5 new measurable lesions may be selected. Larger lesions must be preferred as new measurable lesions over smaller lesions.

- Non-Target Lesions: In alignment with RECIST v. 1.1, Baseline selected non-target lesions can never convert to measurable lesions, not even if they increase in size at subsequent time points and become measurable. Only true new lesions can be measured and contribute to the TMTB.
- All new lesions not selected as new measurable lesions are considered new non-measurable lesions and are followed qualitatively. Only a massive and unequivocal progression of new non-measurable lesions leads to an overall assessment of irRECIST-defined progressive disease (irPD) for the time point.
- Persisting new nonmeasurable lesions prevent irCR.
- In the absence of clinical deterioration, progression should be confirmed no less than 4 weeks after the initial irPD assessment.

### **9.2.7 Tumor Biopsies**

Tumor biopsies will be required during the Screening period, except as indicated in the Inclusion Criteria, (Section 7.2) and at Week 10 (unless the tumor is inaccessible for biopsy). Specific instructions for tumor biopsy and tumor archival sample collection, labeling, storage, packaging, and retention will be provided in the Laboratory Manual.

#### **9.2.7.1 Microsatellite Instability Testing**

Microsatellite instability high (MSH) in tumors refers to changes in 2 or more of the 5 National Cancer Institute-recommended panels of microsatellite markers in tumor tissue. The original (1997) Bethesda guidelines proposed a panel of 5 microsatellite markers for the uniform analysis of MSI in HNPCC. This panel, which is referred to as the Bethesda panel, included 2 mononucleotide (BAT-25 and BAT-26) and 3 dinucleotide (D5S346, D2S123, and D17S250) repeats (Rodriquez-Bigas, 1997). Individual testing sites may utilize a slightly different panel of markers incorporating alternative mononucleotide or dinucleotide markers. Regardless of the panel of markers, samples with instability in 2 or more of these markers are defined as MSI-High (MSI-H), whereas those with one unstable marker are designated as MSI-L. Samples with no detectable alterations are MSS.

Sites should query subject's medical history for prior MSI testing detected by an accredited laboratory per local regulations to select subjects with CRC for non-MSI-H tumors. Non-MSI-H status in potential subjects will be done prior to the Screening period as part of standard diagnostic testing by Investigators. A polymerase chain reaction (PCR) test will be utilized for repeat testing of the non-MSI-H cohort and for testing of responders in other cohorts. Additional tumor samples must be sent to the Sponsor for future confirmatory testing for confirmatory studies of the in vitro diagnostic. A lab manual separate from the protocol will provide detailed information regarding MSI testing and sample requirements.

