## **7.4.3 Colorectal Carcinoma, non-Microsatellite Instability High**

### **Inclusion Criteria:**

- 1) Subject has histologically confirmed metastatic or recurrent colorectal carcinoma;
- 2) Microsatellite instability status low (MSI-L) or microsatellite stable (MSS) as detected by an accredited laboratory per local procedures see Section 9.2.7.1.
- 3) Prior treatment: Progression during, after, or been intolerant following the last administration of approved standard therapies, which must include at minimum a fluoropyrimidine, oxaliplatin, and irinotecan, as well as at least one of the following agents, if approved or in standard national guidelines, bevacizumab, cetuximab or panitumumab (if *KRAS* wild type), or regorafenib.

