**7.4.6 Pancreatic Adenocarcinoma**

**Inclusion Criteria:**

- 1) Subject has histologically or cytologically confirmed locally advanced unresectable or metastatic pancreatic ductal adenocarcinoma;
- 2) Tumor sample available for MSI testing (Note: archived material is sufficient);
- 3) Prior treatment: Subject must have received at least one prior chemotherapy regimen for their disease and must have radiological or clinical progression or documented unacceptable toxicity.

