**Exclusion Criterion:**

- 1) Known microsatellite instability-high (MSI-H) tumor status.

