### **12.3.1 Sample Size Determination**

The sample size for the dose-finding phase of the study is based on a standard 3+3 dose-finding design and depends on observed toxicity. With 2 doses under consideration, a maximum of 12 subjects will be required.

The Simon's 2-stage optimal design will be used for the expansion cohorts. A cohort may be considered for termination due to lack of efficacy if the observed number of tumor responses (either confirmed or unconfirmed) in the first stage is too small. The characteristics of this design depend on 2 probabilities: the false positive rate (FPR), the probability of declaring the experimental treatment to be superior when in fact it is no better than the historical standard, and the false negative rate (FNR), the probability of concluding the experimental treatment to be no better than the historical standard, when in fact it is superior. The table below presents operating characteristics of the Simon's 2-stage design with 15% FPR and 10% FNR for various expansion cohorts and their historical and target objective response

rates. For example, an initial evaluation of efficacy may be performed after 16 treated subjects with squamous cell NSCLC have evaluable tumor response data. Guided by the Futility Boundary as shown, the decision to terminate the cohort or to allow it to continue will be made after taking into consideration other relevant observations such as duration and depth of response and risk/benefit profile. The number of subjects receiving treatment at the time of the Stage 1 efficacy evaluation may exceed the specified Stage 1 sample size depending on accrual rate, response lag, and other factors.

Upon completion of Stage 1 enrollment for a given cohort, the SRC will review available efficacy and safety data and determine whether enrollment into Stage 2 may continue, even if not all response data are yet available to determine whether the Stage 1 criteria have been met. The SRC may decide that enrollment may continue if the benefit risk assessment is perceived to be positive.

With FPR or one-sided alpha=15% and FNR or 1-power=10%.

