**Table 12.3.1-1 Sample Size Estimation by Tumor Type**

Tumor Type	Response Assumptions		Simon 2-Stage Sample Sizes a		Probability of Early Stopping due to Futility (%) if true response rate= Lower Bound
	Lower Bound Historical Response Rate (%)	Target Response Rate (%)	Stage 1 (n1)/Total N	Stage 1 Response Futility Boundary ( $\leq$ ): stop if this many responses or fewer	
NSCLC SQ	20	40	16/32	3	60
NSCLC NSQ PD-L1 non-expressing	10	30	10/21	0	35
Ovarian	10	30	10/21	0	35
CRC (non-MSI high)	5	20	12/29	0	54
SCCHN	25	45	14/36	3	52
HCC	16	36	12/28	6	41
Pancreatic	0	15	15/17	0	>99

a: False positive rate (FPR) or one-sided alpha=15% and false negative rate (FNR) or 1-power=10%.

CRC=colorectal carcinoma; n1=sample size in Stage 1; N=sample size; non-MSI high=non-microsatellite instability high; NSCLC=non-small-cell lung cancer; NSQ=non-squamous; PD-L1=programmed cell death-ligand 1; HCC=hepatocellular carcinoma; SOC=Standard of care; SCCHN=squamous cell carcinoma of the head and neck. SQ=squamous.

A maximum of 188 subjects will participate in the study.

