4.4 Data Sets Analyzed

The following analysis sets will be used in the study:

- **Safety Analysis Set:** Includes all subjects who received at least one dose of IMP (even a partial dose).
- **Efficacy Analysis Set:** Includes all subjects who receive combination therapy in Cycle 1 Day 1.
- **Pharmacokinetic Analysis Set:** Includes all subjects who provide at least one post-dose concentration measurement.
- **Pharmacodynamic Analysis Set:** Includes all subjects who provide at least one post-dose sample.
- **ADA Analysis Set:** The ADA analysis set for mogamulizumab will include all subjects that have both a baseline subject ADA status and at least one on-treatment subject ADA status.

The number of subjects in the Safety Analysis, Efficacy Analysis, Pharmacokinetic Analysis, Pharmacodynamics Analysis Set, and ADA analysis set will be summarized.

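### The PCR repeat test of MSI status in the colorectal cohort has no prespecified role in any efficacy analysis, so a PCR MSI-high responder would count towards the non-MSI-high response rate

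*Protocol*

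**What the plan says.** Entry to the CRC cohort (Protocol Section 7.4.3) requires "Microsatellite instability status low (MSI-L) or microsatellite stable (MSS) as detected by an accredited laboratory per local procedures", and the exclusion criterion rests on the same local basis. Section 9.2.7.1 has sites take this status from testing done before Screening. It then adds the PCR step: "A polymerase chain reaction (PCR) test will be utilized for repeat testing of the non-MSI-H cohort and for testing of responders in other cohorts". The section states no consequence of an MSI-high PCR result.

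The Efficacy Analysis Set (Protocol Section 12.2 and SAP Section 4.4) carries no MSI condition: "Includes all subjects who receive combination therapy in Cycle 1 Day 1". SAP Section 4.9.1 runs every efficacy analysis on that set. MSI appears in the SAP as a baseline characteristic (Section 4.6, Tables 14.1.2.1.1 and 14.1.2.1.2) and in a subject listing (Listing 16.2.4.2). The reasons for replacing Phase 2 subjects (Protocol Section 7.5.1) concern Cycle 1 dosing and safety follow-up, not MSI. Protocol Section 12.9 includes all dosed subjects by default and lets the Sponsor exclude subjects where a protocol violation damages interpretation.

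On design, Protocol Section 12.3.1 says: "The Simon's 2-stage optimal design will be used for the expansion cohorts". The CRC row of Table 12.3.1-1 reads "CRC (non-MSI high) 5 20 12/29 0 54". That is a 5% historical rate, a 20% target, 12 subjects in Stage 1 out of 29, a boundary of 0 responses, and a 54% early-stopping probability.

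The pancreatic cohort (Section 7.4.6) differs. It requires an available tumor sample and excludes only "Known microsatellite instability-high (MSI-H) tumor status".

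**The concern.** The CRC cohort asks whether the combination is active in non-MSI-high disease. The protocol does not rely on the local result alone, since it repeats the test. Yet a subject found MSI-high on the repeat stays, by default, in the numerator and denominator of the response rate for a population to which, on that result, the subject does not belong.

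The only exclusion route is the Sponsor's discretion under Protocol Section 12.9. A subject who was MSI-low or stable locally met the entry criteria as written, so it is unclear that any violation occurred. If the route were used anyway, the decision would be made in an open-label trial with the response already known. Either choice, keeping or dropping the subject, could then be questioned. A rule written in advance removes that problem.

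Other handling in the protocol is tighter. PD-L1 status, which defines the non-squamous lung cohort, is determined centrally before enrollment (Sections 7.4.1.2 and 9.2.7.2). With a historical rate of 5% and a boundary of 0, one response carries much of the evidence in CRC.

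**Working it through.** **Inputs.** From Protocol Table 12.3.1-1 and Section 12.3.1: p0 = 0.05, p1 = 0.20, n1 = 12, N = 29, Stage 1 boundary 0, one-sided alpha 0.15, power 0.90. Stage 1 counts confirmed or unconfirmed responses, with no MSI condition. Two inputs are assumptions, because the documents give no value: the response probability q of an MSI-high subject (0.3 to 0.5) and the per-subject probability m of being MSI-high on PCR (1% to 2%).

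**1. The plan's own figure.** P(0 of 12 at 5%) = 0.95^12 = 0.540, which matches the stated 54%. The chance of exceeding the boundary is 1 − 0.540 = 46.0%. A search for the optimal design under the stated error rates returns the same 12/29 with boundary 0.

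**2. One MSI-high subject present in Stage 1.** P(exceed) = 1 − 0.95^11 × (1 − q), with 0.95^11 = 0.569.
- q = 0.3: 1 − 0.569 × 0.7 = 60.2%
- q = 0.4: 1 − 0.569 × 0.6 = 65.9%
- q = 0.5: 1 − 0.569 × 0.5 = 71.6%

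If that subject responds, the boundary is exceeded with certainty.

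**3. Presence left to chance.** The mixed response rate is p = (1 − m) × 0.05 + m × q, and P(exceed) = 1 − (1 − p)^12.

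| m | q | p | P(exceed) |
|---|---|---|---|
| 1% | 0.3 | 0.0525 | 47.6% |
| 1% | 0.5 | 0.0545 | 49.0% |
| 2% | 0.3 | 0.0550 | 49.3% |
| 2% | 0.5 | 0.0590 | 51.8% |

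**4. The final result.** One subject is 1/29 = 3.4 percentage points of ORR. For illustration, 3/29 = 10.3% with such a responder becomes 2/28 = 7.1% without. The documents do not state a final cut-off. The design search implies that 3 or more responses in 29 would be declared positive, with a false positive rate of 0.148 and power of 0.9005. On that implied cut-off, one MSI-high subject in Stage 1 with q of 0.3 to 0.5 raises the false positive rate to between 0.217 and 0.273.

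**5. Why removal works in CRC but not in pancreatic.** In CRC the PCR is planned for the cohort, so removal need not depend on response. Outside that cohort it is planned for responders only. Removing one MSI-high responder from 17 pancreatic subjects turns 1/17 = 5.9% into 0/16 = 0%, while any untested MSI-high non-responder stays in the denominator. That exclusion is selected on outcome.

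**The case against.** The strongest defense is that the main analysis is already sound. ORR is a secondary endpoint, the primary endpoint is safety, and keeping all treated subjects in the ORR is a conventional choice. This stands, and the full-set ORR should remain the main analysis.

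The information may also be recoverable. The SAP tabulates MSI by assay in the Efficacy Analysis Set by tumor type, lists MSI by subject, and lists best overall response by subject. SAP Section 1 permits additional analyses identified in the study report. This stands in part. The documents do not say whether the MSI fields hold the local or the repeat result, and an analysis added after the responses are seen lacks the force of a planned one.

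The frequency is also unknown and may be small. This stands, and it is why step 3 belongs beside step 2. Nor can one see whether the 5% historical rate itself excludes MSI-high disease, since the tumor-type rationale is blacked out in the public copy.

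Finally, the Stage 1 boundary is guidance only. The Safety Review Committee (SRC) also weighs duration and depth of response and benefit-risk, and may continue before all Stage 1 responses are in. This stands: the percentages above describe the boundary signal, not the decision.

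**Conclusion.** For CRC the gap is real. The cohort is defined by MSI status and the status is retested, but no efficacy analysis uses the result. The size depends on two quantities absent from the documents. The range of 60.2% to 71.6%, against 46.0%, is conditional on one MSI-high subject being in Stage 1. The range of about 48% to 52% holds if each subject has an assumed 1% to 2% chance of being one. The first range should not be read as the expected effect.

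A reader might infer more, and the documents do not support it:

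- **That the pancreatic cohort has the same defect.** It is not labelled non-MSI-high and excludes only known MSI-high tumors. A subject of unknown status is eligible by design, and PCR there may be a first test.
- **That one MSI-high responder opens Stage 2.** The boundary is not binding.
- **That the Stage 1 count should be redone without such subjects.** This would leave fewer than the designed 12, with no revised boundary: 0.95^11 gives 56.9% early stopping against 54.0%. The protocol now plans for data cutoff, and Section 8.1.2.1 disbands the SRC as of Amendment 3, so a recount is probably moot.
- **That the PCR is the Sponsor's own test, or that its results already exist.** The protocol says neither.

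**What to change.** In SAP Section 4.9.1 and the sensitivity table for best overall response (Table 14.2.1.2), prespecify for CRC an ORR with exact 95% CI that removes PCR-confirmed MSI-high subjects from both numerator and denominator. Keep the full-set ORR in Table 14.2.1.1 as the main analysis. Use the primary definition of best overall response for the new row and label it clearly, because Table 14.2.1.2 already carries a different definition that stops at first progression. Subjects without a PCR result stay in. Show how many subjects were tested among responders and non-responders, so that a reader can see whether removal depended on outcome.

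For pancreatic, report the MSI status of responders descriptively and do not remove responders alone from the ORR. Add a matching sensitivity ORR only if MSI results exist for every subject in that cohort.

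The cost is a few table rows and a short SAP paragraph, with no new assays. The downside is that the sensitivity ORR may be slightly lower than the main one. SAP Section 1 says the plan is finalized before database lock, and the rule should be in place by then.
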